2.2 Subject Status Definitions

The subject status definitions utilized in this study are provided in Table 3.

Table 3: Subject Status Definitions

Subject Status	Definition
Provisionally enrolled	
Subject has provided written informed consent but has not yet been screened against the MPP sub-study specific inclusion and exclusion criteria.
 
Provisionally enrolled subjects will become fully enrolled if they meet the MPP sub-study specific inclusion and exclusion criteria, and complete the MPP Enrollment visit.
 
Provisionally enrolled subjects will not be included in the analysis population for the study objectives; however, they may be included in analysis of additional data of interest.

Screen Failure	
Subject has signed consent, but at the time of consent it was identified the subject does not meet all inclusion/exclusion criteria,
 
OR
 
Subject consented prior to implant, but prior to implant the subject status changes.
 
Subject will be exited and will not be included in the analysis population or count toward the enrollment maximum.

Fully Enrolled	
Subject meets all of the MPP sub-study specific inclusion criteria and none of the exclusion criteria, and completes the MPP Enrollment visit.
 
Fully enrolled subjects will be included in the analysis population for the study objectives, as well as in the analysis of the additional data of interest.

2.3 Study Size and Duration

The MPP sub-study will enroll up to 110 subjects at up to 75 sites within the United States who are participating in the QP ExCELS study. Based on the previous sample size analysis for the post-approval QP ExCELS cohort, the sample size for the QP ExCELS study is 1754 and will remain unchanged to support continuation of the MPP sub-study (QP ExCELS protocol version February 1, 2017 provides the justification and sample size analysis).

Subjects that enroll in the MPP sub-study will be followed 12 months post-implant, while subjects that do not continue in the MPP sub-study will be followed for 6 months post-implant.

2.3.1 MPP Sub-Study Sample Size Analysis

The investigation is designed to limit the number of patients involved while still exposing the device to a sufficiently large patient population in order to ensure a representative and statistically meaningful sample.

2.3.1.1 Primary Endpoint 1 Sample Size

The estimated sample size requirements are based on a superiority comparison of the proportion of responders to a performance goal of 3%, chosen based on the assumption that any conversion of non-responders to responders is clinically relevant. A performance goal of 3% was chosen rather than 0% to account for variability (“noise”) around 0%, for example, due to infrequent subjects who are late responders to CRT or improve regardless of MPP. The expected result is estimated at a 10% conversion of non-responders to responders.

There is limited published data available for mid- to long-term follow-up CRT response with multiple point LV pacing in any population. The St. Jude Medical MultiPoint Pacing IDE Study (“St. Jude IDE study”, NCT01786993) evaluated CRT response based on a Clinical Composite Score (CCS) after 3 months of BiV pacing (Tomassoni et al., 2016; System Help Manual, St. Jude Medical). Subjects were then randomized to the MultiPoint™ Pacing treatment arm or to continue on with BiV pacing. The study showed that 70.1% of subjects were responders to MultiPoint™ Pacing. However, both responders and non-responders after 3 months of BiV pacing were included in the MultiPoint™ Pacing treatment arm. Additionally, the St. Jude IDE study only randomized subjects with acute “equal or better” EA velocity time integral (VTI) with MultiPoint™ Pacing vs. BiV pacing per echocardiogram at the 3-Month Visit. There were 52 subjects that did not meet this criterion and were not randomized. Thus, subjects that may likely have not responded to multiple point LV pacing therapy were not randomized which certainly led to a higher response rate to MultiPoint™ Pacing.

BIOTRONIK proposes to allow enrollment of any QP ExCELS subject meeting non-responder criteria (“all-comer non-responders”) at the 6-Month Follow-up into the MPP sub-study as it is not standard of care to perform echocardiograms on CRT subjects to determine if they are responding to standard CRT therapy. As such, we estimate that the proportion of non-responders at 6-months that will be converted to responders at 12-months post-implant will be less than that observed in the St. Jude IDE study. There are three additional studies which have published results for CRT response with MPP measured via CCS or NYHA improvement with mid- to long-term follow-up (6 to 12 months) (Forleo et al., 2016; Pappone et al., 2015; Zanon et al., 2016). However, these studies also did not limit multiple point LV pacing treatment to non-responders, thus the results are not directly applicable to the proposed BIOTRONIK study design.

Assumptions:

- Study Design: Superiority Trial
- Type I error (alpha): 0.025 (one-sided)

- Statistical power: 80%
- Performance Goal: 3%
- Expected: 10%

A total of 90 evaluable subjects would be required to demonstrate superiority to a performance goal of 3%.

2.4 Interim Analysis

An interim analysis will be performed on the primary endpoint when 50% ($n = 45$) of subjects have completed participation in the MPP sub-study. An alpha spending function (DeMets et al., 1994) will be incorporated to make adjustments on alpha for the interim and final analyses. Boundaries will be computed based on the O'Brien-Fleming method. The MPP sub-study will be terminated early and a final report will be prepared if the evidence of benefit reaches significance of $P < 0.0026$ at the 50% interim analysis.

Due to the conservative alpha spending for the interim analysis, the threshold for determining significance at the final analysis is impacted minimally, with a final nominal p-value required for significance being 0.0224. The required sample size is not affected to any meaningful extent by the interim analysis and the sample size for primary endpoint 1 remains unchanged ($n = 90$).

Interim Analysis (50%), significance level, $\alpha = 0.0026$

Type I Error, Final adjusted significance level, $\alpha = 0.0224$

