2.5 Adjustments to Overall Sample Size

Due to the inclusion of interim analyses, a total of 90 evaluable subjects are required to demonstrate superiority to a performance goal of 3%. Assuming a 10% loss to follow-up rate during the study for reasons unrelated to the study outcomes, a total enrollment of 100 subjects would be required to achieve an evaluable study population of 90 subjects.

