2.6 Data Analyses

Descriptive statistics will be used to present and summarize the data collected in the clinical study. Frequency distributions and cross tabulations will be presented for discrete variables. Means, standard errors, and ranges will be presented for continuous variables.

Classification of "HF hospitalization" and "cardiovascular death" events for use in primary endpoint 1, secondary endpoint 2, and secondary endpoint 3 analyses will be determined by a Clinical Events Committee (Section 5.1.1.).

For primary endpoint 1, the lower, one-sided, exact 97.5% bound for the observed proportion of responders ("improved") would have to exceed 3% for rejection of the null hypothesis. Additionally, descriptive statistics will be provided for observed

changes in NYHA class and frequency tabulations provided for the other components of the Clinical Composite Score.

The AE-free rate calculated for secondary endpoint 1 will be based on the total number of subjects with at least one MPP related adverse event requiring additional invasive intervention to resolve. For the secondary endpoint analysis, the AE classification, category, resolution, and relation to the MPP feature for each individual event will be determined by the Clinical Events Committee (CEC) (Section 5.1.1). All adverse events which the CEC determines the event is related or possibly related to the MPP feature will be included in the secondary endpoint 1 analysis. Adverse events with a final CEC adjudicated relation of not related or unknown will not contribute to or be included in the evaluation of the secondary endpoint.

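### The final significance level of 0.0224 in Section 2.4 is not the O'Brien-Fleming value (0.0240), and Section 2.6 tests at an unadjusted 0.025

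*Combined protocol and SAP*

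**What the plan says.** Section 2.3.1.1 sizes the primary endpoint for a one-sided type I error of 0.025, a performance goal of 3%, an expected rate of 10% and 80% power, giving 90 evaluable subjects.

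Section 2.4 adds one interim analysis at 45 subjects. It says an alpha spending function "will be incorporated to make adjustments on alpha for the interim and final analyses", with boundaries from the O'Brien-Fleming method. The sub-study stops for benefit at p < 0.0026. The final analysis is described as only slightly affected, "with a final nominal p-value required for significance being 0.0224", and the same figure is repeated as "Type I Error, Final adjusted significance level".

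Section 2.6 gives the rejection rule for primary endpoint 1: "the lower, one-sided, exact 97.5% bound for the observed proportion of responders" must exceed 3%. It does not mention the interim look.

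The analysed number is not fixed at 90. Section 2.5 says "a total enrollment of 100 subjects would be required to achieve an evaluable study population of 90 subjects". Section 2.3 says "The MPP sub-study will enroll up to 110 subjects". Section 2.6.2 analyses all fully enrolled subjects by intention to treat.

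**The concern.** The sub-study states one hypothesis, and its final success rule is written two ways. A 97.5% one-sided bound is a test at 0.025, the whole design alpha, whereas Section 2.4 asks for 0.0224. If a result fell between the two, someone would have to choose the rule after seeing the data.

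The number in Section 2.4 is also mislabelled. Subtracting the interim level from the total gives the alpha still to be spent at the final look. The nominal p-value for that look is larger, because some results that cross the final boundary would already have crossed the interim one. Calling the remainder a nominal p-value gives away part of the alpha under the name of a method that does not require it.

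**Working it through.** **Inputs.** From 2.3.1.1: one-sided alpha 0.025, null rate 3%, expected rate 10%, N = 90. From 2.4: look at n = 45, interim level 0.0026, final level 0.0224. From 2.6: exact 97.5% lower bound. From 2.5 and 2.3: 100 planned and at most 110 enrolled. The range of 75 to 114 analysed subjects is a reviewing choice that brackets these sizes.

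**1. Plan figures that reproduce.** The exact binomial test at 0.025 first reaches 80% power at n = 90 (7 responders, single-stage power 80.8%). 90 / (1 − 0.10) = 100. The classical O'Brien-Fleming interim level is 0.00258, which rounds to the stated 0.0026.

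**2. Final level.** The interim and final statistics are treated as bivariate normal with correlation √(45/n), which is √0.5 at n = 90. The classical boundary solves

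P(Z₁ ≥ c√2 or Z₂ ≥ c) = 0.025,

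giving c = 1.9774, with nominal levels 0.00258 and 0.0240.

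- With the interim level fixed at 0.0026, the final level is 0.02399.
- The O'Brien-Fleming-type spending function gives 0.0015 and 0.0245.
- None of these gives 0.0224, but 0.0250 − 0.0026 = 0.0224 exactly.

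Large-sample overall alpha at n = 90, with the interim at 0.0026:

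| Final level | Overall alpha |
|---|---|
| 0.0224 | 0.02345 |
| 0.0240 | 0.02501 |
| 0.025 | 0.0260 |

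**3. Responders required.** The smallest k with P(X ≥ k | n, 3%) below the level:

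| Analysed n | 0.025 (Section 2.6) | 0.0240 | 0.0224 (Section 2.4) |
|---|---|---|---|
| 75–93 | 7 | 7 | 7 |
| 94 | 7 | 7 | 8 |
| 95 | 7 | 8 | 8 |
| 96–114 | 8 | 8 | 8 |

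The next sizes at which the 0.025 and 0.0224 rules differ are 73, 74, 115 and 116.

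**4. The disputed results as bounds** (exact lower limits, to be compared with 3%):

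| Result | P(X ≥ 7) at 3% | 97.5% | 97.60% | 97.76% |
|---|---|---|---|---|
| 7/90 | 0.0188 | 3.184% | 3.157% | 3.112% |
| 7/94 | 0.0232 | 3.046% | 3.020% | 2.977% |
| 7/95 | 0.0245 | 3.014% | 2.988% | 2.945% |

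**5. Exact two-stage error and power.** At the interim, P(X ≥ 6 of 45) = 0.00217 at 3%, so 6/45 stops the study. For final threshold k,

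P(reject) = P(X₁ ≥ 6) + Σ over x = 0 to 5 of P(X₁ = x) · P(X₂ ≥ k − x), with X₂ from the remaining n − 45.

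- n = 90, k = 7 under both rules: error 0.0192, power at 10% 80.9%.
- n = 94: power 84.2% under 2.6 (k = 7), 74.0% under 2.4 (k = 8).
- n = 95: power 85.0% under 2.6, 75.0% under 2.4.
- n = 100, k = 8 under both: power 79.7%.
- n = 110, k = 8 under both: power 87.1%.

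The power gaps at 94 and 95 equal the chance of reaching the final analysis with exactly 7 responders: 84.2 − 74.0 = 10.2 points and 85.0 − 75.0 = 10.0 points.

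The largest exact overall error for n = 75 to 114 is 0.0249 with the 97.5% bound, 0.0237 with 0.0240 and 0.0226 with 0.0224.

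**The case against.** The strongest reply is that nothing of consequence turns on this. At 90, 100 and 110 analysed subjects the two rules need the same count. Because the binomial is discrete, even the unadjusted bound keeps the exact overall error within 0.025 throughout the range. A split verdict needs exactly 94 or 95 analysed and exactly 7 responders. Section 2.4 is also the more specific text, so most readers would apply its adjusted level and treat 2.6 as not updated. All of that is fair, and it limits the size of the point. It does not remove the contradiction: 2.6 is where the rejection rule is written, and no sentence ranks the two sections.

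That the sponsor obtained 0.0224 by subtraction is an inference, since the documents give no derivation. The mismatch with the named method does not depend on it.

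Section 2.4 also names a spending function, and that reading gives 0.0015 and 0.0245, so 0.0240 is not the only O'Brien-Fleming candidate. This is correct, but 0.0026 matches only the classical boundary, and neither reading yields 0.0224. What stands is that the spending-function sentence should be tidied with the rest.

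Finally, 94 or 95 can arise in several ways: 5 or 6 lost from 100, or about 105 enrolled with 10% lost (105 × 0.90 = 94.5). The sizes are reachable, though nothing shows that they are likely.

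**Conclusion.** The point holds. Section 2.4's final level does not belong to the method it names, and Section 2.6 states a different success rule for the same hypothesis. In large samples the stated pair uses 0.0235 of the available 0.025, so 0.0224 is conservative. No loss of type I error control is shown under either rule. Within 75 to 114 analysed subjects the two sections disagree only on 7/94 and 7/95. At those two sizes the choice of rule moves power at a 10% rate by about 10 percentage points; at the other sizes in that range it has no effect.

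These figures assume one look at exactly 45 subjects, stopping at 6 or more responders, and exact binomial tests. The correction should be made because this is a confirmatory threshold and the change is small.

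**What to change.** Before primary-endpoint data are seen, keep the interim level at 0.0026 (6 of 45), label it the classical O'Brien-Fleming boundary, and reword the spending-function sentence in 2.4 to agree. State one final level in 2.4 and make its matching exact bound the only final success rule in 2.6. Either choice works:

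- **(a)** 0.0240 with a 97.60% bound; or
- **(b)** 0.0224 with a 97.76% bound, described as deliberately conservative and no longer as the O'Brien-Fleming level.

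Hold the chosen level fixed whatever the final number. For (a), recomputing it at the actual information fraction gives 0.0236 to 0.0243 over n = 75 to 114 and changes no required count.

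The 0.0015/0.0245 pair is not proposed. It would raise the interim threshold from 6/45 (p = 0.00217) to 7/45 and cut the chance of early stopping at a 10% rate from 29.2% to 15.9%.

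The cost is one or two numbers and a short rewording, with no added patients. The 7 responders needed at 90 do not change. Compared with the present 2.6, 7/95 would no longer succeed under either option, nor 7/94 under (b). Under (a), with the look held at 45, large-sample alpha rises from 0.0250 at n = 90 to 0.0253 at n = 114, although the exact error stays at or below 0.0237. Under (b) the corresponding ceilings are 0.0238 and 0.0226.

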2.5 Adjustments to Overall Sample Size

Due to the inclusion of interim analyses, a total of 90 evaluable subjects are required to demonstrate superiority to a performance goal of 3%. Assuming a 10% loss to follow-up rate during the study for reasons unrelated to the study outcomes, a total enrollment of 100 subjects would be required to achieve an evaluable study population of 90 subjects.

2.6 Data Analyses

Descriptive statistics will be used to present and summarize the data collected in the clinical study. Frequency distributions and cross tabulations will be presented for discrete variables. Means, standard errors, and ranges will be presented for continuous variables.

Classification of "HF hospitalization" and "cardiovascular death" events for use in primary endpoint 1, secondary endpoint 2, and secondary endpoint 3 analyses will be determined by a Clinical Events Committee (Section 5.1.1.).

For primary endpoint 1, the lower, one-sided, exact 97.5% bound for the observed proportion of responders ("improved") would have to exceed 3% for rejection of the null hypothesis. Additionally, descriptive statistics will be provided for observed

changes in NYHA class and frequency tabulations provided for the other components of the Clinical Composite Score.

The AE-free rate calculated for secondary endpoint 1 will be based on the total number of subjects with at least one MPP related adverse event requiring additional invasive intervention to resolve. For the secondary endpoint analysis, the AE classification, category, resolution, and relation to the MPP feature for each individual event will be determined by the Clinical Events Committee (CEC) (Section 5.1.1). All adverse events which the CEC determines the event is related or possibly related to the MPP feature will be included in the secondary endpoint 1 analysis. Adverse events with a final CEC adjudicated relation of not related or unknown will not contribute to or be included in the evaluation of the secondary endpoint.

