Sentus QP – Extended CRT Evaluation with Quadripolar
Left Ventricular Leads

EP PASSION/MPP Sub-Study Amendment

Protocol Version – September 6, 2019

PROTOCOL SIGNATURE PAGE

The signature below documents receipt and review of the QP ExCELS study protocol and any attachments, and provides assurance that this study will be conducted according to all stipulations of the protocol, including all statements regarding confidentiality, and according to local legal and regulatory requirements and applicable guidelines.

Principal Investigator:

Name (please print)

Signature

Date

Summary

Title	Sentus QP – Extended CRT Evaluation with Quadripolar Left Ventricular Leads EP PASSION/MPP Sub-Study Amendment
Acronym	QP ExCELS
Subject collective	Heart failure subjects with standard CRT-D indication according to clinical routine.
Design	Single-arm, multi-center, and prospective trial. The MPP sub-study is designed to fulfill the FDA required post-approval study for the US market released BIOTRONIK MultiPole Pacing (MPP) feature (PMA P050023/S107) of the Ilivia HF-T QP family CRT-D system (PMA P050023/S103), or Acticor/Rivacor HF-T QP family CRT-D system (PMA P050023/S125).
Objectives	The primary objective of this clinical investigation is to convert a percentage of CRT non-responders to responders using the MultiPole Pacing (MPP) feature.
Primary Endpoint	Evaluation of the CRT responder status with the MPP feature
Secondary Endpoints	
 1. Freedom from MPP system-related complications at 6 months post MPP enrollment. 2. Clinical composite score + patient global assessment responder status 3. Clinical composite score responder status utilizing a modified responder classification
Sample Size	QP ExCELS study: up to 1,754 subjects enrolled in U.S. MPP sub-study: up to 110 subjects within the U.S. who are participating in the QP ExCELS study.
Investigational Sites	Up to 75 sites within the United States
Follow-up period	All subjects will be followed up to 6 months for screening into the MPP sub-study. If the MPP inclusion/exclusion criteria are met at screening, the subject will be followed an additional 6 months.
Sponsor	BIOTRONIK, Inc. Clinical Studies Department [name]

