2.6.1 Replacement of Missing Data

The last observation carried forward (LOCF) principle will be utilized for the analysis of NYHA Classification and Patient Global Assessment for primary endpoint 1 and secondary endpoints 2 and 3.

Missing NYHA and patient global assessment data at either the enrollment or follow-up visits affects the number of subjects that can be included in the analysis. It is possible that subjects or study personnel may either forget or choose not to answer one or more of the questions related to NYHA classification or patient global assessment.

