2.6.2 MPP Sub-Study Analysis Population

The primary and secondary endpoint analyses will be conducted according to the intention-to-treat principle (ITT) utilizing all available data from fully enrolled subjects. Subjects are expected to remain programmed with the MPP feature ON from MPP enrollment through the completion of the sub-study. Subjects who have the MPP feature permanently turned OFF prior to completion of the sub-study will be required to report a protocol violation; however, these subjects will be included in the analysis population. All available data from subjects that undergo a pulse generator change and no longer have an MPP eligible device will be included in the analysis. Subjects may have the MPP feature temporarily turned OFF due to a lead revision procedure and these short durations with MPP will not be reported as a protocol violation.

Any QP ExCELS subject that does not enroll into the MPP sub-study but receives MPP due to the physician's determination will not be analyzed towards the MPP study endpoints.

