3.4.2.2 Withdrawal of subject consent

Subjects may withdraw their consent for study participation at any time without stating the reason and without any unfavorable consequences. All data, which are collected until the date of withdrawal will be used for analysis. A Study Termination eCRF has to be completed by the investigator in which the reasons for withdrawal should be documented if willingly provided by the subject.

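### The 6-month AE-free rate has no stated denominator, censoring rule or interval; read naturally it is a crude proportion that understates 6-month risk, most after an early stop

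*Combined protocol and SAP*

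**What the plan says.** The Summary defines Secondary Endpoint 1 at a fixed time: "Freedom from MPP system-related complications at 6 months post MPP enrollment". Section 2.6 is the only place that describes the estimate. Its sentence begins "The AE-free rate calculated for secondary endpoint 1 will be based on the total number of subjects" and, read to its end, makes the rate "based on the total number of subjects with at least one MPP related adverse event requiring additional invasive intervention to resolve", which is a count of subjects with an event, as adjudicated by the Clinical Events Committee. It names no denominator, time-to-event method, censoring rule or interval.

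Three other sections bear on the denominator:

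- Section 2.6.2 runs the primary and secondary analyses "according to the intention-to-treat principle (ITT) utilizing all available data from fully enrolled subjects".
- Table 3 in Section 2.2 makes a subject fully enrolled once the MPP criteria are met and the MPP Enrollment visit is done. No minimum follow-up applies, and "Fully enrolled subjects will be included in the analysis population for the study objectives".
- Section 3.4.2.2 covers subjects who withdraw: "All data, which are collected until the date of withdrawal will be used for analysis".

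The missing-data rule in Section 2.6.1 is last observation carried forward "for the analysis of NYHA Classification and Patient Global Assessment for primary endpoint 1 and secondary endpoints 2 and 3". It does not reach Secondary Endpoint 1.

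Section 2.4 plans one interim analysis, at 45 completers. If the boundary is crossed, "The MPP sub-study will be terminated early and a final report will be prepared". It does not say what happens to subjects who are then between MPP enrollment and their 6-month visit.

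**The concern.** The target is a risk over a fixed 6 months, but the only ingredients the plan gives are a count of events and a set of subjects with no required follow-up. Dividing one by the other gives every subject the same weight, whatever the time observed. Someone lost at one month without an event contributes as a full 6-month success, and events that would have occurred later are never seen. The error runs in one direction, towards a safer-looking feature.

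This is the only safety endpoint of a post-approval study required by FDA. Two analysts could follow the text and report different rates from the same data. The gap matters most after an early stop, when a large share of the enrolled subjects could have only part of their follow-up.

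**Working it through.** **Plan figures used.** The documents give no sample size, expected rate or goal for Secondary Endpoint 1. The figures they give for the primary endpoint set the scenarios, and they reproduce:

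- Exact binomial, 3% against 10%, one-sided 0.025, N = 90: at least 7 responders are needed, type I error is 0.0188 and power is 0.8075. This agrees with 90 evaluable in Section 2.3.1.1.
- 90 / (1 − 0.10) = 100 enrolled, as in Section 2.5. The ceiling in Section 2.3 is 110.

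**Assumptions not in the documents.** Constant hazard; true 6-month risk r = 4%; partial follow-up uniform over 0 to 6 months.

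**Mean observed risk in a subject with partial follow-up.** Averaging 1 − exp(−λt) over 0 to 6 months, with λ = −ln(1 − r)/6, gives

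a = 1 − r / [−ln(1 − r)] = 1 − 0.04 / 0.04082 = 0.0201.

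**Expected crude rate.** With c complete and m partial subjects it is (c·r + m·a)/(c + m). The relative understatement is 1 minus that rate divided by r.

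| Scenario | Complete | Partial | Crude rate | Relative understatement |
|---|---|---|---|---|
| Planned completion, 10% loss | 90 | 10 | 3.80% | 5% |
| Early stop, ongoing subjects cut off | 45 | 10 | 3.64% | 9% |
| same | 45 | 20 | 3.39% | 15% |
| same | 45 | 45 | 3.01% | 25% |
| same | 45 | 55 | 2.91% | 27% |

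For the first row: (90 × 0.04 + 10 × 0.0201)/100 = 0.0380. For the last: (45 × 0.04 + 55 × 0.0201)/100 = 0.0291. The documents give no accrual rate, so the number of partial subjects at a stop is unknown.

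**Sensitivity to the assumed risk.** The relative figures barely move. With 90 complete and 10 partial, true risks of 2%, 5% and 10% show as 1.90%, 4.75% and 9.51%. With 45 complete and 55 partial they show as 1.45%, 3.64% and 7.30%.

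**How likely is an early stop?** Under the 3% goal, 6 responders of 45 give exact P = 0.0022, which is below 0.0026. Five give P = 0.0110, which is not. So at least 6 are needed. The probability of that is 29% at the plan's expected 10% conversion, 69% at 15% and 91% at 20%.

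**The case against.** A reader might infer that the plan declares subjects with incomplete follow-up to be event-free. It does not. The sentence in Section 2.6, read to its end, describes the numerator; stopping at the words about the total number of subjects makes it look like a denominator. Section 2.6.2 fixes the population, not the estimator, and a Kaplan-Meier estimate on the same population would not contradict it. That much stands: the bias follows from the natural reading and is not a stated rule.

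A reader might also infer that an early stop produces a 25% understatement. Section 2.4 does not say that ongoing subjects are exited, and Section 3.4.2 asks for every effort to keep following them. If they finish their 6 months, the early-stop component disappears. Even if they are cut off, the size depends on accrual, which is why a range is given.

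The absolute effect is modest. With 45 complete and 45 partial, the shortfall is 90 × (4.00% − 3.01%), about 0.9 expected events. The exact 95% interval for 3 events in 90 subjects runs from 0.7% to 9.4%, so sampling error is larger than the bias. Nor is this endpoint all the safety information: Section 2.1.5 lists other adverse-event data, and Section 5.1 puts further events in the clinical report.

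Finally, Kaplan-Meier is not beyond criticism here. Death is a competing event in heart failure, and censoring deaths tends to overstate the cumulative incidence of complications. The fix has to address this.

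These points limit the size and force of the concern. They do not supply the missing denominator or follow-up rule.

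**Conclusion.** The point holds as a gap in specification whose natural reading is biased in a known direction. The plan sets a 6-month quantity but gives no denominator, no handling of incomplete follow-up and no interval.

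Under the assumptions above, a crude proportion over all fully enrolled subjects understates a 4% risk by 0.2 percentage points (about 5% relative) with the planned 10% loss. If the sub-study stops early and ongoing subjects are cut off, the understatement is about 9% to 27% relative for 10 to 55 partial subjects.

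The documents support neither a stated rule that early leavers are event-free nor a certain large bias after a stop. The endpoint has no hypothesis or performance goal, so the consequence is for the bias and precision of a descriptive safety rate. No test decision is affected. This is a cheap improvement and not a serious defect.

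**What to change.** In Section 2.6:

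- Report Secondary Endpoint 1 as the Kaplan-Meier AE-free rate at 6 months (180 days) from MPP enrollment with a 95% interval, censoring subjects without an event at last contact.
- Show the crude proportion beside it, with its denominator stated.
- As a check, add a cumulative-incidence estimate with death as a competing event.

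In Section 2.4, state whether subjects still in follow-up at an early stop complete their 6 months and, if not, how they enter this endpoint.

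The cost is a little analysis work and a slightly less favourable rate. No new data are needed: Section 8.1.2 already requires adverse event dates, and Section 3.4.3 defines the termination date for early exits, including deaths.
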